## 2.6 Design and Procedures

### 2.6.1 Study Design

Single-center, randomized, double blinded, parallel-group, 2-cohort investigation. Patients receive standard monitoring for anesthesia and postoperative care. Surgical and anesthesia care (except for intraoperative opioid use) are not altered for study purposes. In each cohort, subjects are randomized 1:1 to either typical short-duration or long-duration opioid.

### 2.6.2 Randomization

Subjects in each cohort will be randomized 1:1 to either short-duration or long-duration opioid using randomization tables generated by the hospital Investigational Pharmacy. Each subject is assigned the next number. Anesthesia practitioners are instructed on study procedures, and receive a sealed envelope with Group (drug) assignment and group-specific instructions. To ensure full double-blinding, subjects, investigators, and study team members evaluating patients will be blinded to drug treatment. Dropouts (after treatment) will not be replaced, in case this is not random but outcome-related. Enrollment is increased to account for dropouts.

### 2.6.3 Preoperative

Patients will complete a questionnaire about current pain, past 7 day average pain, pain interference with activities of daily living, and expected level of postoperative pain (NIH PROMIS-29 Profile v2.0, PROMIS Global Health Scale 1.2, <http://www.nihpromis.org/>). Quality of life indices will be assessed using the Veterans RAND 12-item health survey (VR-12), the Barthel index of activities of daily living, and the Quality of Recovery QoR-15. Demographic data will be recorded. Additional questions will query patients' current employment, level of normal activities, and expectation of time to return to work and normal activities. Demographic data including patient zip codes, employment status, education status, will be recorded. Patient information (demographics, medical history, procedure, medications, pain scores) will be extracted from patient's electronic medical records.

### 2.6.4 Intraoperative and postoperative care and study drug administration

Anesthesia and surgical care are not altered for this study, except for randomization to intraoperative and recovery room opioid (all opioids are currently used as part of standard anesthesia care). Anesthetic induction and maintenance are per usual, and at practitioners' discretion.

Patients in the short-duration opioid group receive typical short-duration opioids (IV fentanyl, morphine, and/or hydromorphone), given as needed throughout the intraoperative period, at practitioners discretion, per usual practice. Patients in the long-duration opioid group receive IV methadone HCl 15 mg in "short-stay" patients (1.5 cc of 10 mg/ml) (10 mg, 1.0 cc if  $\leq 55\text{kg}$ ) and 10 mg in "same-day" patients (1 cc of 10 mg/ml)). These subjects receive methadone only as their intraoperative opioid, given as a single bolus at anesthetic induction.

For analgesia in the Post-Anesthesia Care Unit (recovery room, PACU), patients in the short-duration group continue to receive typical short-duration opioids (fentanyl, morphine, hydromorphone), at practitioners discretion. It is not necessary that patients receive the same short-duration opioid postoperatively as intraoperatively. Methadone patients continue to receive methadone (2 mg increments). Post-op opioids are given by PACU MDs and nurses, based on patient pain reports, per standing orders and institutional practice.

Practitioners will have the discretion to administer additional opioid at the end of surgery on emergence, while still in the operating room or during transport, to ensure patient comfort. Patients in the short-duration group would continue to receive typical short-duration opioids (fentanyl, morphine, hydromorphone), and patients in the long-duration group would receive methadone. For study purposes, these will be recorded as PACU doses.

Approximately 24 ml of blood will be collected from an existing IV catheter for later genotyping (CYP2B6 or pain-related genes). Genotyping will be performed by an appropriate laboratory

As a safety measure, in the remote event that patients experience repeated respiratory-specific PACU events or at PACU discharge, they will be sent to a monitored (pulse oximetry) bed ('short-stay' cohort) or observed in the PACU for additional time ('same-day' cohort).

### 2.6.5 Post-Discharge

Post-discharge care is not altered for purposes of this study. Both groups in both cohorts will receive standard of care post-discharge analgesics as determined by their treating surgeon. These include NSAIDs and opioids (oxycodone, oxycodone+acetaminophen (Percocet, Tylox), hydrocodone+acetaminophen (Norco, Vicodin), tramadol, and codeine+acetaminophen (Tylenol#3)). Selection and quantity of opioids dispensed will be at surgeons' discretion.

Opioids will be dispensed in a medication monitoring system, to measure drug utilization during the 30d post-discharge follow-up period. After discharge, patients record their pain self-assessments, home opioid use, and side effects each day through emailed REDCap or paper surveys, allowing real time data recording. Additional REDCap surveys will be emailed at 6 and 12 mo.

For approximately 30d postop, patients will be queried once daily (evening) regarding pain (average at rest, with activity, with coughing, using NRS), pain relief and pain interference with eight activities of daily living (5-point Likert scale) using the NIH PROMIS Pain Intensity 3A and Pain Interference 6A questionnaires. Recovery is assessed using the QoR-15. Patients also record opioid and non-opioid analgesic use, sedation, and time to return to work and ADLs, and opioid side effects (ORSDS). This electronic-based system has improved daily data capture, improved reliability, and can trigger patient contact if necessary to ensure maximal data capture.

### 2.6.7 Observations and Measurements

All assessment scales are the standard in perioperative methodology, and are conducted by a trained member of the research team, blinded to randomization allocation. Assessments are conducted after PACU admission, every 15 min for the first hour, hourly for the next 4 hr, at bedtime, and ~24 hr after surgery or prior to hospital discharge (whichever is first), using established protocols. We use the standard, well-defined, reliable, recommended patient-reported outcome measures to assess pain. Pain intensity is assessed (at rest/while coughing/with activity) using the validated 0-10 Numeric Rating Scale (NRS). Pain relief is assessed using the standard 5 point scale (none=0, slight=1, moderate=2, good=3, complete=4). Observed sedation (Modified Observer's Assessment of Alertness/Sedation, MOAA/S) and subject's self-assessment of sedation are recorded concurrently with pain assessments. Opioid side effects are assessed prior to discharge using the Opioid-Related Symptom Distress Scale (ORSDS). ORSDS uses 4-point Likert scales to characterize 12 opioid side effects (nausea, vomiting, constipation, difficulty urinating, difficulty concentrating, drowsiness, dizziness, confusion, fatigue, itchiness, dry mouth, and headache) according to frequency, severity, and bothersomeness. Twelve symptom-specific ORSDS scores (0-4) are the average of the 3 distress dimensions (frequency, severity, and bothersomeness). The composite ORSDS (0-4) is the mean of the 12 individual scores. ORSDS has both construct reliability and content validity. Drug administration for prophylaxis/treatment of opioid side effects (e.g. antiemetics) during hospitalization is recorded from the electronic medical record. Particular attention will be paid to opioid-related adverse events, most importantly respiratory depression. During PACU recovery, four types of respiratory-specific events will be assessed:

1. Hypoventilation (3 episodes of <8 respirations/min)
2. Apnea (episode of apnea  $\geq 10$  seconds)
3. Hypoxemia (3 episodes of oxyhemoglobin saturation  $<90\%$  for 30 sec with/without nasal oxygen)
4. "Pain/sedation mismatch" (defined as MOAA/S 0-2 and a numeric pain score  $> 5$ )

Postoperative opioid use will be quantified from the medication monitoring system, patients' daily questionnaire, and residual pill counts, and recorded both as the number of tablets used and total morphine equivalents using standard opioid conversion tables.

Recovery from surgery/anesthesia will be assessed at 7d, 14d, 21d, 30d, 6mo and/or 1yr postoperatively, by assessing patient-reported quality of life, functional independence, health status, and ability to return to work and normal activities. We will assess quality of life (Veterans RAND 12-item health survey VR-12, functional independence (Barthel index of activities of daily living, recovery (QoR-15). QoR-15 assesses 5 domains of patient-reported health status: pain, physical comfort, physical independence, psychological support and emotional state using an 11-point numerical rating scale with results summed from 0 (poor recovery) to a maximum of 150 (excellent recovery). These are among the most commonly used instruments, are extensively validated and normed, and are our hospital standards, used locally for several years. Thus we can compare postop with preop metrics, but also with our entire patient database. VR12 is a short form based on the Veterans SF36 version, has 2 domains and 8 dimensions leading to 12 questions, and generates two aggregate summary scores (Physical Component & Mental Component summaries), which are standardized using weights derived from the general population survey and calibrated so that 0.50 is the threshold defining the status of the respondent. Washington University has standing approval ([name]) to use the VR12 and scoring algorithm. The Barthel questionnaire assesses functional independence (able to complete 10 specific normal activities like bathing, feeding, dressing, with any help). It generates a weighted aggregate score 0-100 (100=highest independence). We will evaluate patients' return to employment (defined as work for pay or volunteer work outside home). If applicable, specific questions targeting the reason (pain, addiction, etc) for not returning to work will be asked at 30d, 6mo and 1yr.

Throughout the investigation, any adverse events will be described, recorded and reported according to GCP and IRB regulations.

Medical records are used to calculate the amount of morphine equivalents administered during surgery and until discharge, as well as other drug administration for treatment and/or prophylaxis of possible opioid side effects.

Baseline measurements that will be obtained from patients or the medical record are age, sex, ethnicity, vital signs, weight, height, and peripheral oxygen saturation by pulse oximetry.

Subjects will be compensated \$400 for the time and effort to complete 1-30d daily data entries, and use and return of medication monitoring pill bottle, and 6 and 12mo survey responses.

#### Patient Surveys/Self-Assessments

	Baseline	Discharge	Daily POD 1-3	Daily POD 4-30	POD 7	POD 14	POD 21	POD 30	6 mo	12 mo
PROMIS Global Health Scale 1.2 08.22.2016	✓							✓	✓	✓
PROMIS -29 Profile 2.0	✓							✓		
RAND VR12 v4	✓				✓	✓	✓	✓	✓	✓
Barthel Index ADLs	✓				✓	✓	✓	✓	✓	✓
QoR-15	✓	✓	✓		✓	✓	✓	✓		
PROMIS Pain Intensity 3A v1.0					✓	✓	✓	✓		
PROMIS Pain Interference 6A v1.0					✓	✓	✓	✓		
OSPREY Survey-Baseline	✓									
OSPREY Survey 1 mo								✓		
OSPREY Survey 6 mo									✓	
OSPREY Survey 12 mo										✓
Home diary				✓	✓					

### 2.6.8 Primary and secondary outcome measures

Primary outcome measure: Total 30d post-discharge home opioid use (number of tablets). This is because surgeons prescribe a variety of post-op opioids (oxycodone, tramadol, oxycodone+acetaminophen, hydrocodone+acetaminophen, codeine+acetaminophen), we avoid any confounding by use of opioid conversion tables, and the most important factor in opioid diversion and misuse is the number of left-over tablets.

Secondary outcome measures:

1. Total 7d post-discharge home opioid use (number of tablets).
2. Total intraoperative non-methadone opioid administration
3. Total PACU opioid administration
4. Total hospital non-methadone opioid administration

Exploratory outcomes:

1. Total day of surgery nonmethadone IV opioid administration
2. Total day of surgery nonmethadone IV and oral opioid administration
3. Total day of surgery opioid administration
4. Postoperative day 1 total IV oral and opioid administration (for short-stay cohort only)
5. Total hospital opioid administration
6. PACU pain scores (NRS) and pain relief score; at time-specific intervals
7. Duration of intraoperative analgesia (median time to request for re-medication with opioid)
8. PACU side effects and adverse events: respiratory depression (4 events occurrence per above), sedation (MOAA/S score), nausea/vomiting (number of events); at time-specific intervals and total
9. PACU duration of stay
10. 7d and 30d total post-discharge home opioid use (in morphine equivalents)
11. 7d and 30d post-discharge pain scores (NRS) and pain relief score; daily
12. Total pain relief (TOTPAR), calculated as the area under the curve of pain relief score vs time
13. 7d and 30d post-discharge opioid side effects (ORSDS); daily, weekly and total (summed and average)
14. Time to cessation of post-discharge opioid use
15. 7d and 30d post-discharge unused opioid tablet count
16. Quality of recovery at 7d, 14d, 21s, 30d, 6 mo, and/or 12 mo (VR-12, Barthel index, QoR-15, functional independence, return to work)
17. Surgeons' opioid prescribing patterns

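### Secondary outcome 2 is zero by design in adherent methadone patients, and secondary outcome 4 is tilted toward a reduction because it omits that arm's operating-room and PACU methadone

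*Combined protocol and SAP*

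**What the plan says.** Section 2.6.8 and the Synopsis name four secondary outcomes. The second is "Total intraoperative non-methadone opioid administration" and the fourth is "Total hospital non-methadone opioid administration". Two exploratory outcomes use the same exclusion: "Total day of surgery nonmethadone IV opioid administration" and "Total day of surgery nonmethadone IV and oral opioid administration".

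Section 2.6.4 fixes which opioid each arm may receive. Usual care is unchanged "except for randomization to intraoperative and recovery room opioid". For the methadone arm it states: "These subjects receive methadone only as their intraoperative opioid, given as a single bolus at anesthetic induction". Extra opioid on emergence or in transport is methadone in that arm and a short-duration opioid in controls, and of both it says: "For study purposes, these will be recorded as PACU doses". In the PACU the methadone arm continues on methadone, and controls continue on fentanyl, morphine or hydromorphone.

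Section 2.8 (Aim 1) compares opioid consumption before discharge and says that intraoperative and in-hospital use will be evaluated by a suitable model, separately in each cohort. It does not say how the non-methadone outcomes should be read.

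**The concern.** An outcome can show an effect of treatment only if it is free to vary in both arms. Here the assignment decides which drug is given, and the outcome definition then leaves out the drug given to one arm. A difference would appear even if methadone had no effect on need.

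Two of the four secondary outcomes are affected. Section 2.2 already reports the pilot results as lower intraoperative and later opioid requirement, so outcomes 2 and 4 could easily be reported in the same terms. The hospital total that includes methadone is only exploratory outcome 5. No sample size rests on outcomes 2 or 4.

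**Working it through.** The plan states no expected effect or sample size for outcomes 2 or 4, so there is no plan figure to reproduce. The inputs are 187 randomised per arm (Synopsis), 150 evaluable per arm (section 2.4) and the dosing rules in section 2.6.4.

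**Step 1. Which doses count in an adherent patient**

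| Stage | Control: outcome 2 | Methadone: outcome 2 | Control: outcome 4 | Methadone: outcome 4 |
|---|---|---|---|---|
| Intraoperative | counted | 0 | counted | 0 |
| Emergence or transport (booked as PACU) | – | – | counted | 0 |
| PACU | – | – | counted | 0 |
| PACU exit to discharge | – | – | counted | counted if non-methadone |

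Outcome 2 is identically zero in the methadone arm. For outcome 4:

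difference (methadone − control) = true post-PACU difference − control mean (intraoperative + PACU)

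In the same-day cohort the post-PACU window ends on the day of surgery. An adherent methadone patient given nothing after the PACU scores zero on outcome 4 as well.

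**Step 2. Outcome 2: how little is needed for significance.** All methadone patients are set to 0, and k controls receive any intraoperative opioid.

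- Rank-sum, 187 per arm: k=3 gives p=0.083; k=4 gives p=0.045.
- Fisher, 187 per arm: k=5 gives p=0.061; k=6 gives p=0.030.
- As shares of the arm: 4/187 = 2.1% and 6/187 = 3.2%. The same counts apply at 150 per arm (4/150 = 2.7%, 6/150 = 4.0%).

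Departures from assignment rarely undo this. The table gives the largest number of methadone patients who could also receive non-methadone opioid with two-sided Fisher p still below 0.05. The control proportions are assumptions.

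| Controls with any (of 187) | Methadone patients with any (of 187) |
|---|---|
| 187 (100%) | 181 (97%) |
| 178 (95%) | 166 (89%) |
| 168 (90%) | 153 (82%) |
| 140 (75%) | 121 (65%) |
| 94 (50%) | 74 (40%) |

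**Step 3. Outcome 4: what a built-in difference does.** Assume equal post-PACU use, equal SDs and a normal approximation. The difference d, in SD units, that gives a stated chance of a significant reduction is d = (1.96 + z) × √(2/n).

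- n=187, √(2/187) = 0.1034: 50% chance 1.96 × 0.1034 = 0.203; 80% chance 2.80 × 0.1034 = 0.290; 90% chance 3.24 × 0.1034 = 0.335.
- n=150, √(2/150) = 0.1155: 0.226, 0.323 and 0.374.

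The documents do not place the trial on this scale. As an illustration, set control PACU use to the pilot methadone groups' figures in section 2.2 (4 ± 5 mg short-stay, 2 ± 3 mg same-day), ignore control intraoperative opioid, and use 150 per arm. With an assumed post-PACU SD s, SE = √[(SD_PACU² + 2s²)/150]. For short-stay and s = 10 mg, SE = √(225/150) = 1.22 and Φ(4/1.22 − 1.96) = 90%.

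| Assumed post-PACU SD | Short-stay (−4 mg built in) | Same-day (−2 mg built in) |
|---|---|---|
| 5 mg | 99.99% | 89% |
| 10 mg | 90% | 40% |
| 20 mg | 40% | 14% |

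Counting control intraoperative opioid would enlarge the built-in difference.

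**Step 4. Why totals that include methadone need a range of conversion factors.** Take outcome 3 (total PACU opioid). Suppose true use is equal in both arms at the pilot figures and all methadone-arm PACU opioid is methadone. A factor f times the reference scales that arm's mean μ and SD by f. Solve |μ(f − 1)| / √[SD²(f² + 1)/187] = 1.96:

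- short-stay (4, 5): f = 1.293 or 0.773;
- same-day (2, 3): f = 1.364 or 0.733.

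A factor 29% higher or 23% lower (36% or 27% in same-day) would make equal use look significantly different.

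**The case against.** The strongest reply is that both outcomes are openly labelled non-methadone. A difference in that quantity is real, and it misleads only if read as sparing or need. Section 2.8 names no test for either outcome, so the rank-sum and Fisher thresholds rest on tests chosen for this check. The SD scale for outcome 4 is a general power formula. Secondary outcome 3 includes methadone at the same rank, and exploratory outcomes 3, 4, 5 and 7 also help. A sentence on interpretation might do most of the work.

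Much of this stands. The labels are honest, the size of the outcome 4 bias is unknown, and outcome 3 does cover the PACU. But an honest label does not make the comparison informative for Aim 1. Outcome 4 does not isolate supplementary need either, because the methadone arm's PACU top-ups go uncounted. Outcome 3 stops at PACU exit and needs a methadone conversion factor that the documents do not state. Section 2.6.7 mentions standard conversion tables, but in the context of home opioid use. Section 2.6.8 itself gives avoidance of conversion tables as a reason for counting tablets in the primary outcome.

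**Conclusion.** The concern holds, with high confidence, and should be fixed. Outcome 2 is zero by design under adherence. A test of it reflects the control arm's own dosing and any departures from assignment, some of which may reflect unmet need. Outcome 4 is shifted toward a reduction by the control arm's mean intraoperative plus PACU dose. Exploratory outcomes 1 and 2 share the flaw.

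The result for outcome 2 rests only on the dosing rules and the definition. The size of the shift in outcome 4 cannot be computed, because the control intraoperative dose and the post-PACU mean and SD are not given. Higher post-PACU use in the methadone arm could offset it. The illustrative percentages depend on equal need, pilot PACU figures from methadone patients and assumed SDs. The primary outcome, secondary outcome 1 and the sample size are untouched.

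**What to change.** Amend the outcome lists in the Synopsis and section 2.6.8:

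1. Report outcome 2 descriptively by arm, with no efficacy test.
2. Base the outcome 4 comparison on opioid given from PACU exit to discharge, the only in-hospital window in which assignment does not set the type of opioid. Beside it, show total postoperative in-hospital opioid including methadone, in morphine equivalents over a stated range of methadone conversion factors. Use the same range for outcome 3.
3. Treat exploratory outcomes 1 and 2 as descriptive.
4. Keep exploratory outcome 5 as supportive, because it contains the fixed methadone bolus and depends on the conversion factor.

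The cost is a protocol amendment, any registry record brought into line (section 5.7) and a short sensitivity analysis. No new data are needed, since section 2.6.7 already takes morphine equivalents from surgery to discharge from the medical record, and no treatment rule changes.

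There are two downsides. PACU exit is a post-randomisation time and PACU stay may differ by arm, so the post-PACU figure should be read with the postoperative total. Post-PACU use may also be sparse in the same-day cohort.

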#### **2.4. Overall study design**

Both trials (“short-stay” and “same-day” surgery cohorts) will test the same hypothesis, and have the same protocol aims, inclusion and exclusion criteria, procedures, assessments, methods of data analysis, and hypothesis testing, but are otherwise separate (and separately analyzed). Two cohorts are studied because their operations may have different pain intensities and opioid requirements. The protocol is very similar (hypothesis, aims, inclusion/exclusion, procedures, assessments, data analysis, hypothesis testing) to that of the dose-finding Pilot (Preliminary Studies). In each cohort, patients will be randomized to general anesthesia with methadone or short-duration opioids. Patients are followed in-hospital, then queried daily for 30d after discharge through emailed REDCap or paper surveys. Additional REDCap surveys will be emailed at 6 and 12mo.

Target enrollment is 300 evaluable subjects per cohort (150 control, 150 methadone). A 25% overall drop-out rate prior to 30d follow-up is conservatively assumed, thus 375 subjects in each cohort will be studied (750 total).

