### 2.8 Hypothesis testing

For all Aims, the two cohorts ("short-stay" and "same-day" surgery) are analyzed separately. Subgroup analysis may also explore specific surgical procedures (procedure-specific analgesia).

Aim 1: Compare the influence of methadone vs short-duration opioids on short-term (before discharge) and intermediate term (1-30d post-discharge) opioid consumption.

30d post-discharge opioid use ( $> 5$  pills) will be compared between arms using Chi-square tests and multiple logistic regression, with opioid group as a predictor and adjusting for the important clinical and demographic covariates. Total pill consumption will be compared using GEE model with Poisson link function. In addition, a time-to-event (survival) model will be fit to compare time to opioid discontinuation between the two groups.

adjusting for the appropriate covariates. Opioid use during intraop, in-hospital post-op, and post-discharge periods will be evaluated using appropriate model and data transformation, depending on the distribution of the data. It is common in some analgesic trials that subjects dropping from different treatment groups differ with respect to reasons for early discontinuation (i.e. not random but outcome-related). Therefore analysis will not be “completers only”. Drop-out rates will be compared between the drug groups, and 30d opioid consumption ( $>5$  vs  $\leq 5$  pills) analyzed with and without drop-outs. Drop-outs will be censored at the time of dropping out in time to discontinuation analysis. A corollary of opioid consumption by patients is opioid prescribing by surgeons. It is possible that surgeons’ prescribing practices (# tablets per patient) may change during the study (coincidentally or as a result thereof) and this will be explored.

**Aim 2:** Compare methadone vs short-duration opioids in reducing short-term (immediate postoperative), intermediate term (1-30d post-discharge), and chronic (6-12 mo) postoperative pain.

Pain reduction effectiveness of methadone vs short-duration opioids will be compared using repeated measures models to adjust for multiple measures on each subject. Depending on the distribution of NRS, VAS and pain relief data, data will be analyzed as normal, or transformed into an ordinal or other scale.

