**Aim 3:** Evaluate major and bothersome short-term (before discharge) and intermediate term (1-30d post-discharge) opioid-related side effects with methadone vs short-duration opioids.

Side effects (respiratory-specific events, composite ORSDS) will be compared between the groups using Chi-squared or Fisher exact test, as appropriate, and using logistic models to adjust for important clinical and demographic covariates.

**Aim 4:** Compare overall recovery after surgery/anesthesia with methadone vs short-duration opioids, as defined by changes in reported Health-related Quality of Life, functional independence, and ability to return to work and normal activity.

Overall recovery will be assessed using chi-square tests for categorical outcomes and t-tests for continuous outcomes as well as a repeated measures model to adjust for multiple time points.

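### If diary completeness differs by arm, raw 30-day ORSDS sums and averages can show a false side-effect difference; Aim 3 should use a repeated-measures model of the daily scores

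*Combined protocol and SAP*

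**What the plan says.** - **Outcome.** Section 2.6.8, exploratory outcome 13, and the same item in the Synopsis: "7d and 30d post-discharge opioid side effects (ORSDS); daily, weekly and total (summed and average". Neither says how a sum or average is formed when days are missing, or whether the average divides by days recorded or days scheduled.
- **Source of the scores.** Section 2.6.5, describing the daily query over about 30 days: "Patients also record opioid and non-opioid analgesic use, sedation, and time to return to work and ADLs, and opioid side effects (ORSDS". Section 2.6.7 gives the scale: "The composite ORSDS (0-4) is the mean of the 12 individual scores".
- **Analysis.** Section 2.8, Aim 3: "Side effects (respiratory-specific events, composite ORSDS) will be compared between the groups using Chi-squared or Fisher exact test, as appropriate". Covariate-adjusted logistic models are added. No cut-point is given for this 0-4 mean score, and no longitudinal model is named.
- **Comparable outcomes.** Pain under Aim 2 "will be compared using repeated measures models to adjust for multiple measures on each subject". Aim 4 also names a repeated-measures model, for recovery.
- **Incomplete follow-up.** Section 2.4: "A 25% overall drop-out rate prior to 30d follow-up is conservatively assumed". Section 3.0 expects less than 15%. The specific drop-out measures sit under Aim 1 and concern opioid use: "Drop-out rates will be compared between the drug groups, and 30d opioid consumption" is analysed with and without drop-outs, and drop-outs are censored in the time-to-discontinuation analysis.

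**The concern.** A total over 30 diary days is a fair patient-level summary only when all 30 days are there. On partial diaries, a sum over recorded days in effect scores each missing day as zero. An average over recorded days weights whichever days the patient happened to return, and for a patient who stops early those are the early days, when symptoms are probably worst. The two summaries can therefore err in opposite directions for the same patient.

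Within one arm this is noise and a shift in level. It matters for the comparison when completeness, or its pattern, differs between arms, because part of the arm difference then reflects diary return and not symptoms. Side effects from day 1 to day 30 after discharge are half of Aim 3, and the trial's hypothesis includes side effects that are no worse with methadone. Two listed summaries that can disagree, with no rule for choosing between them, also leave room for selective reporting.

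**Working it through.** The plan states no level, time course, standard deviation or diary-completion figure for ORSDS, so there is no figure of its own to reproduce. Inputs from the documents are 30 daily scores, 187 patients per arm in each cohort (Synopsis), 25% drop-out budgeted and under 15% expected. Everything else below is an assumption.

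**1. One patient, symptoms decaying to zero.** Let the score on day d be proportional to exp(-(d-1)/7). The sum over k days is (1 - exp(-k/7)) / (1 - exp(-1/7)).
- Full 30 days: 0.986 / 0.1331 = 7.41; average 7.41/30 = 0.247.
- Diary stops after day 7: 0.632 / 0.1331 = 4.75; average 4.75/7 = 0.678.
- The sum is 4.75/7.41 = 64% of its full value. The observed-day average is 0.678/0.247 = 2.75 times its full value.

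**2. One patient, symptoms decaying to a floor.** Let the score be 0.2 + 1.3 exp(-(d-1)/7), so 1.5 on day 1. The full sum is 15.63 and the average 0.521. Stopping after day 14 gives a sum of 11.24 (-28%) and an observed-day average of 0.803 (+54%). Divided by 30, the average would be 0.375, which is too low.

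**3. When the observed-day average is not too high.** A flat course gives 0% error. A rising course stopped at day 14 gives -31%. The floor course with days 1-4 missing gives -22%, and with every third day missing +4%.

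**4. Two arms, days skipped at random.** The sum scales with the share of days recorded, whatever the course. For 10% vs 20% skipped, the ratio of sums is 0.90/0.80 = 1.125, a false difference of 12.5%. It applies equally to 7-day and 30-day sums. The average is unaffected.

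**5. Two arms, simulated false-positive rates.** There is no true arm effect, 187 patients per arm, a two-sided 5% comparison of mean per-patient totals, and a stop day spread evenly over the diary period.

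| 30-day setting | Sum | Observed-day average |
|---|---|---|
| Equal drop-out (15%, 20% or 25% in both arms) | 5-6% | 5% |
| Drop-out 10% vs 5% | 5% | 7-10% |
| Drop-out 25% vs 15% | 6-7% | 11-18% |
| Drop-out 20% vs 10%, floor course | 10-11% | 15-16% |
| Drop-out 35% vs 15%, flat course (stress case) | 47% | 4% |
| Skipped days 20% vs 10% | 63-68% | 5% |

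Under the floor course, the 20% vs 10% drop-out gap moves the mean sum by 0.52-0.57 (about 3-4% of 15.63) and the mean average by about 0.03 (about 6% of 0.521), in opposite directions.

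**6. Seven-day totals.** With stop days spread over the 30 days, even 35% vs 15% drop-out moves the 7-day sums by under 2% and the averages by about 1%, with false positives of 5-6%. Skipped days are the main route to bias here, through the ratio in step 4.

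**7. Adjusting for day.** Adding up day-specific arm means, a simple stand-in for a model with arm, day and arm-by-day, brought false positives to 4.8-6.0% in the drop-out and skipped-day settings tried. Missingness there was unrelated to symptoms.

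**The case against.** The strongest reply is that the bias needs an imbalance that nobody forecasts. A reader might infer from section 2.8 that drop-out is expected to differ between arms. It does not say so: it speaks of drop-outs differing in their reasons, and it plans to compare the rates, so an imbalance would be seen. Subjects are blinded, the survey system can prompt contact, and payment is tied partly to daily entries. Section 3.0 also puts about 10 points of its under-15% figure down to changed operations, altered stays and withdrawal. That leaves roughly 15 - 10 = 5% for loss during follow-up, so a 35% arm is a stress case only. All of this stands.

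Three further points stand in part.
- **Direction of the average.** It is tempting to say that partial diaries always make the average too high. Step 3 shows otherwise, and the documents do not fix the denominator.
- **Both time windows.** It is also tempting to treat the 7-day and 30-day totals alike. Drop-out barely touches the 7-day totals.
- **The planned test.** Aim 3 names categorical tests, not a comparison of mean totals, so the simulated error rates describe one natural use of the totals and not a stated analysis. But the plan does not say how the totals enter inference, and a categorical cut of a biased total would inherit the bias, by an amount that cannot be computed without a cut-point.

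The outcome is exploratory, and the daily and weekly scores also listed would help to expose uneven completeness. That limits the weight of the point. It does not supply a method for the totals.

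**Conclusion.** The concern holds conditionally. The plan names summed and averaged totals from a daily diary, has no rule for missing days, and gives this repeated outcome no longitudinal model, although pain and recovery each have one. The following conclusions are supported:

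- Incomplete diaries alone do not create an arm difference. With equal drop-out, error rates stayed nominal.
- If completeness differs by arm, the raw 30-day sum is biased low in the less complete arm. The 7-day sum is affected mainly by skipped days.
- If, in addition, symptoms fall, the missing days are late and the divisor is observed days, the 30-day average is biased high in that arm, opposite to the sum.
- At 25% vs 15% drop-out, false-positive rates are about 6-7% (sum) and 11-18% (average). At 20% vs 10% skipped days they are about 63-68% and 5%.

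The error rates rest on assumed ORSDS courses and between-patient spread. A similar ten-point drop-out gap under the floor course gives 10-11% for the sum. A reader might conclude that the trial will report a spurious side-effect difference. The documents do not support that, because they predict no imbalance. For an exploratory outcome this is a worthwhile and inexpensive improvement, and it leaves the primary analysis untouched.

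**What to change.** In Aim 3, make the between-arm comparison of post-discharge ORSDS the difference in mean daily composite score over days 1-7 and over days 1-30. Estimate both from one repeated-measures model on all available daily scores, with arm, day and arm-by-day, as Aim 2 already does for pain. If a total is wanted, report the model mean times 7 or 30. Keep raw sums and averages in exploratory outcome 13 as descriptive only, state their denominator, and show diary completeness by arm and day beside them.

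The cost is a few lines of SAP text and a type of model that the team already plans to fit, on data already collected. The downside is the assumption that diary days are missing at random given the observed scores. The model does not remove bias from drop-out driven by symptoms that were never recorded, which is close to the outcome-related drop-out that section 2.8 itself raises. The completeness display and the recorded reasons for discontinuation should be read with that in mind.
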